Aim 1a. and 1b. The outcome measures involved in this aim (e.g., parenting self-efficacy measured using the PMP S-E and perceived stress scale), are derived from multi-item scales and will be treated as continuous measurements. For each scale, the mean score after baseline will be assessed at each of the visits (1 week, 1 month, 3 months, 6 months and 12 months). The overall mean difference from baseline for each of the scales between the two intervention groups will be used to evaluate Aim 1. We will assess the overall change in scores for the self-efficacy and depression scales, i.e. the population averaged effect of the intervention on changes in self-efficacy and depression, using a generalized estimating equation (GEE) model to account for the correlation between the repeated change measurements among primary care givers. The GEE model is reasonably robust to missing data. We will use an exchangeable correlation structure, but in sensitivity analyses, will also test unstructured correlation and compare parameter estimates. The main independent variable in these analyses is intervention group, however we will also include (if necessary) a cross-product term of group-by-time which will enable us to estimate differences between the intervention groups over time. The group-by-time term will be included only if it is statistically significant. The model will include covariates reflecting the randomization stratification variables, and other covariates only if imbalances are observed in the randomization groups at baseline. In addition, we will use the model to plot the change in parental self-efficacy or parenting stress over time-by-group with 95% CI around each time point estimate. The degree of change at 3-months will allow us to assess the rapidity of any effect of intervention and a descriptive comparison of the differences between the groups at 6- and 12-months will allow us to assess the degree of persistence of any effect. We will consider the difference between groups to be statistically significant when the 95% confidence intervals around the difference do not include 0.

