Aim 2a. and 2.b. will compare measures of anxiety using the STAI, and depression using the CES-D in primary caregivers from the intervention and control groups. The independent variable will be the intervention group in both models. If necessary, the models will include covariates known to impact parental depression and anxiety (if different between the groups) and stratification variables. We will estimate and compare the covariate adjusted mean difference in the scores between the intervention

groups using GEE models as described above (Aim 1). The difference will be considered to be statistically significant if the 95% CI around the difference fails to include 0.

As in Aim 1, group-by time-interaction models will be used to evaluate differences between the groups over time.

Aim 3. The NICU graduates may experience multiple ED visits or hospitalizations any time after baseline. The number of ED or hospitalization counts will be summed for each of the intervention groups. To assess differences between the intervention groups for each of the outcomes (ED visits or hospitalizations), we will use the Wilcoxon–Mann–Whitney two-sample rank-sum test, which is appropriate for use with nonparametric data, such as the count data from this aim. We will define the outcome, improved immunization status, as receipt of two diphtheria-tetanus-acellular pertussis (DTaP) vaccines, two Hemophilus influenzae b (HIB) vaccines, and two pneumococcal conjugate vaccines (PCV-13) by the end of the observation period (12 months after baseline). This binary outcome will be contrasted using an unpaired t-test with unequal variances to measure the hypothesis that the intervention results in improved immunization status.

Sensitivity Analyses. In sensitivity analyses, we will explore the effect of departures from assumptions made for the main analysis. A key assumption in our analyses is that missing data are missing at random, and groups who are and are not lost to follow-up are similar. We will compare characteristics of families who are, and are not, lost to follow-up. If significant differences between these two ( $p < 0.05$ ) are observed, we can test for intervention effects, but with the assumption that individuals with missing data have worse outcomes. We will then report these ‘worst case’ scenarios and report any changes in the clinical interpretation of the trial.

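### Aim 1 keeps the group-by-time term only if it is significant, yet reads speed and persistence of effect by visit from the model and does not define the overall contrast when the term stays in

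*SAP*

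**What the plan says.** The Aim 1a and 1b paragraph under Statistical Considerations is the same in the SAP and the protocol. It gives these instructions:

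- The measure for the aim: "The overall mean difference from baseline for each of the scales between the two intervention groups will be used to evaluate Aim 1".
- The purpose of the interaction: it is "a cross-product term of group-by-time which will enable us to estimate differences between the intervention groups over time".
- The retention rule: "The group-by-time term will be included only if it is statistically significant". No test, degrees of freedom or significance level is given for it, and time is not said to be categorical or linear.
- Output by visit: "we will use the model to plot the change in parental self-efficacy or parenting stress over time-by-group with 95% CI around each time point".
- Speed of effect: "The degree of change at 3-months will allow us to assess the rapidity of any effect of intervention".
- Persistence: a "descriptive comparison of the differences between the groups at 6- and 12-months will allow us to assess the degree of persistence".

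The paragraph also says that mean scores will be assessed at each visit, but it does not say that the 3-, 6- and 12-month readings come from those means.

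The Aim 2 paragraph says "As in Aim 1, group-by time-interaction models will be used to evaluate differences between the groups over time", without repeating the condition, and judges the result by this rule: "The difference will be considered to be statistically significant if the 95% CI around the difference fails to include 0". It plans no plot and no reading of speed or persistence.

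**The concern.** The plan names the interaction as the means of estimating group differences over time, makes it conditional on a significance test, and then uses by-visit results as if it were always present. Each branch of the rule leaves a problem.

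**Term dropped.** A model without group-by-time has one group difference, common to 1 week and 1, 3, 6 and 12 months. Within-group change can still vary by visit if time is a main effect, but the intervention effect cannot. A non-significant interaction does not show a constant effect, and the stated power calculations are for main outcomes, not for this test. The modelled 12-month difference is then the average over all visits, with the narrower interval of that average. An effect that has largely faded can be shown as lasting.

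**Term kept.** The plan wants an overall mean difference but gives no weights, reference visit or time coding. A single group coefficient in an interaction model is the difference at the reference visit or time origin, and its value changes with that choice.

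For Aim 2 only two points are open: whether the condition applies (the Aim 1 paragraph lists depression among the scales it models), and which contrast the confidence-interval rule tests.

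**Working it through.** **Inputs from the documents** (Sample Size & Power): 150 per group, five post-baseline visits, within-subject correlation r = 0.5. **Assumed**, because the documents give none: the effect patterns, a 0.05 level for the interaction (0.10 and 0.01 also shown), equal visit variances, and complete data.

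**Standard errors, in SD units.**
- One visit: √(2/150) = 0.1155.
- Average of five visits: √[(2/150) × (1 + 4 × 0.5)/5] = √0.008 = 0.0894.

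**The plan's own figure.** The plan states 93% power for 0.33 SD. From 0.33/0.0894 = 3.69, power is 90.2% at two-sided 0.05/3 and 94.1% at one-sided 0.05/3. The stated figure is close to what a visit average gives, with the sidedness unstated. Nothing below depends on it.

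**Chance that the term is dropped.** For visit differences d_j with mean d̄, the 4-df test has noncentrality Σ(d_j − d̄)² / [2(1 − r)/n]. Main pattern 0.4, 0.4, 0.3, 0.2, 0.1 (mean 0.28): 0.068/0.006667 = 10.2. The term is dropped in 27% of trials (18% at level 0.10, 50% at 0.01). With 120 per group the noncentrality is 8.16 and the drop rate 39%. For r from 0.3 to 0.7 the drop rate runs from 44% to 7%. With linear time it is 12–16%, depending on coding.

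**What the by-visit estimates then do.** Simulation of the two-stage rule: SE 0.0894 if the term is dropped, 0.1155 per visit if kept; 4-df test at 0.05.

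| Assumed pattern (SD) | Noncentrality | Dropped | 95% CI coverage over all trials at 3 / 6 / 12 months |
|---|---|---|---|
| 0.40, 0.40, 0.30, 0.20, 0.10 | 10.2 | 27% | 94% / 92% / 82% |
| 0.40, 0.35, 0.30, 0.25, 0.20 | 3.75 | 70% | 94% / 92% / 84% |
| 0.55, 0.45, 0.30, 0.20, 0.10 | 19.95 | 4% | 95% / 94% / 93% |

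In the first pattern, when the term is dropped, the model shows about 0.28 SD at 12 months against a true 0.1 SD, and its interval covers 0.1 in 48% of those trials. Over all trials the 12-month interval excludes 0 in 31%, against 14% if the term is always fitted. At interaction level 0.10, 12-month coverage is 87%. With linear time at 0.05 it is 87–90%.

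**What the overall effect means when the term is kept** (first pattern).

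| Contrast reported | Value (SD) | 95% CI excludes 0 |
|---|---|---|
| Group coefficient, reference 1 week | 0.40 | 93% |
| Group coefficient, reference 12 months | 0.10 | 14% |
| Equally weighted visit average | 0.28 | 88% |

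With linear time, the coefficient at time zero is 0.52 (visit number), 0.40 (months) or 0.34 (log months).

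**Fitted example.** One simulated trial had a true effect of 0.33 SD at the first three visits, 0.25 at 6 months and 0.165 at 12 months. The exchangeable GEE without interaction gave 0.223 at all five visits. With interaction it gave 0.295, 0.323, 0.208, 0.123 and 0.164.

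**Type I error under no effect, nominal 5%.** About 5.0% if the visit average is always tested; 5.4% if a reference-visit coefficient is used when the term is kept; 7.7% if any of the five visit intervals may count once the term is kept.

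**The case against.** The 6- and 12-month comparison is called descriptive, in a clause that does not name the model, and the planned intervals may be for each group's own change and not for the difference between groups. Visit means will be available. The interaction model has to be fitted in order to test the term, and the Aim 2 wording suggests that such models are used for differences over time in any case. The term overall mean difference points to an average, so a reference-visit coefficient would be a misreading. The effect patterns are invented, and a single cross-product term may mean linear time, where the harm is milder. Over all trials the average 12-month bias in the main pattern is only about 0.03 SD. If the effect is truly constant, the rule keeps coverage at about 95% and lowers the root mean squared error at 12 months from 0.115 to 0.094 SD.

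Much of this stands. The coverage figures apply to a between-group difference read from the model, the 3-month reading is barely affected, and a strong fade is rarely missed. But the plot is explicitly taken from the model, the retention rule is explicit, and the Aim 2 cross-reference does not cancel it. A descriptive estimate should still describe its own visit. An average over visits is the likely intention for the overall effect, but the weights and time coding remain unstated.

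**Conclusion.** The concern holds. That dropping the term forces one modelled difference at every visit, and that keeping it leaves the overall contrast unspecified, follow from the text and need no assumed numbers. The size of the harm does rest on assumptions. For moderate fades under a 4-df test at 0.05, 12-month coverage falls to 82–84%. For the main pattern with linear time it is 87–90%. For a strong fade tested with 4 df it stays at 93%. The damage falls mainly on the 12-month persistence reading and on the definition of the Aim 1 contrast. The test of the overall effect is sound provided the visit average is always what is tested. This should be corrected before analysis. For Aim 2 it is a matter of wording only.

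**What to change.** In the Aim 1 paragraph of both documents:

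- Delete the condition on the group-by-time term. Always fit visit as a category with group-by-visit.
- Define the primary effect for each scale as the equally weighted average of the visit-specific group differences, tested once. Use five visits for the PMP S-E, the stress scales and the STAI state scale, and four for the CES-D, which the protocol does not give at 1 week.
- Report the 3-, 6- and 12-month differences with confidence intervals from the same model as descriptive, whatever the interaction p-value.

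In the Aim 2 paragraph, add one sentence stating that the same unconditional model and averaged contrast apply.

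The cost is rewording two IRB-approved documents; no new data are needed. With complete data the averaged contrast equals what the plan's exchangeable model without interaction estimates, and its SE is the same (0.089 SD). Under assumed monotone dropout leaving 60–80% at 12 months, the SE is 0.1–0.9% larger.

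### Free improvement: always adjust the Aim 1 and Aim 2 models for the baseline score, instead of analysing change (Aim 1) and leaving baseline to an imbalance rule

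*SAP*

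**What the plan says.** The SAP text for Aims 1a and 1b (repeated word for word in the protocol's Statistical Considerations) sets the target: "The overall mean difference from baseline for each of the scales between the two intervention groups will be used to evaluate Aim 1". The GEE is used "to account for the correlation between the repeated change measurements among primary care givers", so the outcome is change. The stratification variable is always in the model. Anything else enters under the rule "other covariates only if imbalances are observed in the randomization groups at baseline", and no threshold for imbalance is given. On the interaction: "The group-by-time term will be included only if it is statistically significant". The later visits get "a descriptive comparison of the differences between the groups at 6- and 12-months". The decision rule is "We will consider the difference between groups to be statistically significant when the 95% confidence intervals around the difference do not include 0".

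The Aim 2 text points back to the Aim 1 GEE but differs in two ways. Its target is a covariate-adjusted difference in scores, not in changes, and the stratification variables enter only where judged necessary. It adds: "As in Aim 1, group-by time-interaction models will be used to evaluate differences between the groups over time". The Aim 1 paragraph itself mentions change in depression, so the CES-D is described both ways.

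The protocol's list of assessment tools has every Aim 1 and Aim 2 scale measured at baseline. Follow-up is at five visits, except for the CES-D, which has four (no 1-week visit). Neither document names the baseline score as a prespecified covariate.

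**The concern.** A change score subtracts the whole baseline value, however weakly baseline predicts follow-up. Regression on baseline subtracts only as much as the data support. With baseline and follow-up on the same scale and equal SDs, regression is never less precise, and it is clearly more precise when the correlation is moderate. Here baseline is taken in the NICU and follow-up runs to 12 months at home, so a moderate or low correlation is plausible. The families have already supplied the data that would sharpen the parent outcomes, and the plan uses them inefficiently.

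The imbalance rule recovers only part of the loss. It brings the baseline score in for some randomizations and not others, on a criterion that is not written down.

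There is also a smaller gap in definition. If group-by-time is kept, the group coefficient depends on how time is coded: it is one visit's difference under reference-visit coding, or the difference at time zero under continuous time. The plan does not say how the overall difference is then formed.

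**Working it through.** **Inputs.** From the SAP's Sample Size & Power section: 150 per group, 0.33 SD, up to five post-baseline measures, correlation r = 0.50 among them, alpha 0.05 divided by 3, stated power 93%. From Aim 1: the 95% CI rule, which amounts to two-sided 5%. Assumed: equal SDs at all visits and full follow-up (no dropout rate is stated). The baseline-to-follow-up correlation b is not given and is varied from 0.3 to 0.6.

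**Formulas.** For the mean of k visits, in units of SD²:

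- follow-up scores, unadjusted: S = (1 + (k−1)r)/k
- change from baseline: S + 1 − 2b
- baseline-adjusted: S − b²

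Adjustment gains (1−b)² over change and b² over unadjusted scores. SE = √(2 × factor/150). Power is two-sided normal.

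**The plan's 93%.** With k = 5 and r = 0.5, S = (1 + 4×0.5)/5 = 0.60. At b = 0.5 change also gives 0.60 + 1 − 1 = 0.60. SE = √(1.2/150) = 0.0894. Power is 90.2% at two-sided 0.0167, 94.1% at one-sided 0.0167 and 92.6% at two-sided 0.025. The stated 93% is thus met approximately, but only under a variant that the plan does not name. That is a separate matter.

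**Aim 1, five visits, 95% CI rule.**

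| b | factor: change | factor: adjusted | power: change | power: adjusted |
|---|---|---|---|---|
| 0.3 | 1.00 | 0.51 | 81.5% | 97.9% |
| 0.4 | 0.80 | 0.44 | 89.2% | 99.1% |
| 0.5 | 0.60 | 0.35 | 95.8% | 99.8% |
| 0.6 | 0.40 | 0.24 | 99.5% | >99.9% |

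At b = 0.5 the half-widths are 1.96 × 0.0894 = 0.175 SD and 1.96 × √(0.70/150) = 0.134 SD. An adjusted analysis of 150 × 0.35/0.60 = 87.5, about 88 per arm, matches 150 per arm on change. At two-sided 0.0167 the powers are 90.2% against 99.3% (b = 0.5) and 67.9% against 94.6% (b = 0.3).

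**Aim 2.** If it models change, the table applies to the five-visit STAI state scale. If it models post-baseline scores, the comparison at b = 0.3 is 0.60 against 0.60 − 0.09 = 0.51, or 95.8% against 97.9%. For the CES-D, k = 4 gives S = 2.5/4 = 0.625. At b = 0.5 both change and unadjusted scores have factor 0.625, against 0.375 adjusted: power 95.1% against 99.7% on either reading.

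**The imbalance rule.** No threshold is stated, so three were assumed and simulated, with 40,000 trials per setting at the 5% level. They admit the baseline score in about 5%, 20% and 39% of trials.

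| Analysis | power, b = 0.5 | power, b = 0.3 | null error, b = 0.5 |
|---|---|---|---|
| trigger p < 0.05 | 96.7% | 83.4% | 3.9% |
| trigger p < 0.20 | 98.0% | 87.6% | 3.1% |
| trigger standardized difference > 0.1 | 98.8% | 91.4% | 3.1% |
| always adjusted | 99.8% | 97.9% | 5.2% (b = 0.5) |

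A looser trigger narrows the gap but does not close it. The data-driven rule is conservative under the null.

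**Overall contrast.** For an illustrative profile of 0, 0.15, 0.33, 0.33 and 0.33 SD over the five visits, the equally weighted average is 1.14/5 = 0.23 SD and a time-weighted average is 0.31 SD. The 1-week difference is 0 and the 12-month difference is 0.33 SD. The choice of contrast therefore matters when effects vary over time.

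**The case against.** **The practical effect may be small.** If the stated 0.50 also holds between baseline and follow-up, power moves only from 95.8% to 99.8%. The large gaps need b nearer 0.3, which the documents neither state nor exclude. This stands as a limit on the size. It leaves the narrower interval at b = 0.5, and full follow-up is itself optimistic. With an illustrative 120 per arm and b = 0.4, the SEs are √(1.6/120) = 0.115 and √(0.88/120) = 0.086, giving power of 81.5% against 97.1%.

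**Aim 2 is not simply Aim 1 again.** Its wording on scores and on stratification variables differs. A reader might carry the full (1−b)² gain over to Aim 2; the text does not support that. The gain over change belongs securely to Aim 1 alone.

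**A reader might infer bias or an underpowered trial.** Neither follows. A chance baseline difference of 0.2 SD would shift the change estimate by (1−0.5) × 0.2 = 0.10 SD at b = 0.5. Such differences average to zero over randomizations and are already counted in the variance. No inflation of type I error was found.

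**A reader might infer that the interaction rule changes the hypothesis tested.** The plan names the overall difference as the Aim 1 target, calls the 6- and 12-month comparison descriptive, and says that interaction models serve to describe differences over time. The overall test can fairly be read as coming from the model without the interaction. Keeping the term only if significant suggests a single model, so a clarification is worth asking for, but no error is shown. Equal visit weights are also a preference: three of the five visits fall in the first three months of a 12-month aim.

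**Conclusion.** The point holds as an efficiency improvement that needs no new data. For Aim 1, always adjusting for baseline lowers the variance by (1−b)²: from 0.60 to 0.35 at b = 0.5, and from 1.00 to 0.51 at b = 0.3. For Aim 2 the baseline score is likewise not a fixed covariate, but the gain is b² if scores are modelled. The figures assume equal SDs, r = 0.5 among follow-ups, full follow-up and the stated range for b. The planned analysis remains valid and, at r = b = 0.5 with full follow-up, adequately powered. The undefined contrast when group-by-time is kept is a secondary clarification.

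**What to change.** In every Aim 1 and Aim 2 model, always include that scale's baseline score, the birth-weight stratum and visit. Remove the choice of covariates by observed imbalance. The GEE can stay.

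Specify that the baseline score is the one taken before randomization. The protocol's Consent and Recruitment section lists the surveys first. Its data collection section says only that baseline follows enrolment in the NICU, and the intervention section randomizes within 24 hours and tells controls their assignment. Add a rule for a family with a missing baseline score.

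As a clarification, name one overall contrast over the scheduled post-baseline visits (four for the CES-D, five for the other scales) as the deciding test, whether or not group-by-time is kept. Fix the visit weights in advance; equal weights are one option and time-weighting is another. Report visit-specific differences as secondary.

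The cost is matching edits to the Aim 1 and Aim 2 text in the SAP and protocol, and a little programming, settled before outcomes are compared by group. No new families, visits or instruments are needed. With full follow-up, the equally weighted average has the same variance with or without the interaction, so fixing it costs no power.

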The evaluation of the Parent Navigation NICU to home program will use a randomized trial design. We will do so by recruiting a population of parents who have an infant in the Children's National NICU, half of whom will receive enhanced usual care by provision of a NICU care notebook and half of whom will receive the same enhanced care- including care notebook- plus Parent Navigation (intervention). All will be patients in the NICU who are discharged from the CNMC NICU. Group assignment will be by randomization, stratified by birth weight (≤ 1500 grams or >1500 grams). The design incorporates extensive measurement of baseline attributes to assess the comparability of intervention and enhanced control groups at inception.

We aim to enroll $n=300$ parents of infants receiving care in the Children's National NICU who are discharged from the CNMC NICU. CNMC has a Level IV NICU which receives a large number of complex cases. To allow for generalization of study findings to other NICUs and other centers, we will enroll all patients discharged from the CNMC NICU.

Study personnel will identify eligible NICU patients by reviewing NICU census data or through the use of the PowerTrials Prescreening function. PowerTrials is a HIPAA-compliant application that is integrated into the Children's National Cerner electronic medical records system (PowerChart). Study inclusion and exclusion criteria will be used to create a Prescreening Rule. A screening engine in PowerChart will compare the criteria to patient data within the medical records system, and a list of potential study subjects will be generated.

Research study staff will approach parents anticipating discharge within 1-2 weeks to invite their participation and, as appropriate, obtain informed consent. If parents of eligible patients are not available, we may contact a parent by phone to set up a time to discuss the study in person. We will obtain in person signatures of consent as appropriate before enrolling potential participants in the study. Recruitment will continue in this fashion until the required sample is enrolled.

Inclusion criteria include:

NICU patients discharged from the CNMC NICU. One parent participant per NICU patient will be identified and enrolled as the participant.

Exclusion criteria include:

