The CESD is a measure to identify depression and is administered at baseline, 1 month, 3 months, 6 months and 12 months. The score is tabulated in redcap, and a report identifies scores of 10 or greater. If a participant has a score of 10 or greater on the CESD, the research team leadership (one of the PIs or co-investigators) will contact the participant by phone within 1 week to discuss the elevated score. Please see telephone script for elevated CESD. The team member will then send a letter and resources to the family. Please see attached letters and information sheet detailing perinatal mental health resources. If a participant cannot be reached by phone, a letter with resources will be sent. If a participant has a subsequent score of 10 or greater on the CESD, a follow up letter and resources will be mailed within one week of the elevated score.

Procedures for data collection will be the same for intervention and control group participants. We will have text telephone technology (TTY) available for phone interviews for participants with hearing impairment. RAs will be fully trained on interview procedures and will be supervised by Drs. [name] and [name].

Assessment tools include (all are uploaded in Documents section):

1) Perceived Maternal Parenting Self-Efficacy (PMP S-E) tool: 20 items. Mothers' perceptions of their ability to parent (maternal parenting self-efficacy) are a critical mechanism guiding their interactions

with their preterm newborns. A robust measure is needed which can measure mothers' perceptions of their ability to understand and care for their hospitalized preterm neonates as well as being sensitive to the various levels and tasks in parenting. This will be administered at baseline, 1 week, 1 month, 3 months, 6 months and 12 months post NICU discharge.

2) State-Trait Anxiety Inventory (STAI). This consists of 20-items total, and respondents indicate transitory anxiety on a 4-point Likert scale. The STAI has been used extensively in both medical and non-medical populations, with excellent psychometric properties. The inventory contains the State Inventory (10 items, scale Y1), which will be administered at baseline and 1 week, 1 month, 3 months, 6 months and 12 months post NICU discharge. The trait inventory (10 questions, Y2) will be administered only at baseline.

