**GPS (Giving Parents Support): Parent Navigation After NICU Discharge**

**NCT02743472**

**Statistical Analysis Plan**

**Updated/approved by Children's National IRB: 2/15/17**

**PI: [name], MPH**

### **Statistical Considerations:**

We will conduct intent-to-treat analyses to assess effects of the PN intervention such that randomized families will be analyzed according to their assigned intervention group, regardless of departures from the randomized intervention. While it is possible that families may seek some type of parental support independently of the intervention, these potential effects may be evaluated in sensitivity analyses. Our analysis strategy will first compare baseline characteristics between the PN and control groups to evaluate the balance produced by randomization. It is expected that randomization with stratification on one key confounder of birth weight ( $\leq 1500$  grams or  $>1500$  grams) will result in a balanced distribution of factors between the PN and care resource groups on most, if not all factors. However, even with randomization some imbalance may occur on a few factors and it is important to identify such factors, as these are the ones that need to be controlled during analysis.

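### Aim 1 and Aim 2 covariates enter only if the arms differ at baseline, so the model is selected on chance imbalance, is not fixed in advance, and gives up some precision

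*SAP*

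**What the plan says.** The SAP's Statistical Considerations (repeated in the Protocol section of the same name) set the order of work: "Our analysis strategy will first compare baseline characteristics between the PN and control groups to evaluate the balance produced by randomization". Of any factors found imbalanced, the text says "it is important to identify such factors, as these are the ones that need to be controlled during analysis".

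For Aim 1 the model always carries the stratification variable, and "other covariates only if imbalances are observed in the randomization groups at baseline". For Aim 2 the sentence is: "If necessary, the models will include covariates known to impact parental depression and anxiety (if different between the groups) and stratification variables". Read literally, this makes even the birth-weight stratum conditional in Aim 2.

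The analysed outcome is change from baseline. The GEE is there "to account for the correlation between the repeated change measurements among primary care givers". The baseline score is subtracted but is not named as a covariate.

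Neither document lists candidate covariates or gives a test or cut-off for imbalance. The p<0.05 under Sensitivity Analyses concerns families lost to follow-up, not baseline balance.

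The Protocol's list of assessment tools puts social support (MSPSS), the NICU stress scale (PSS:NICU), the infant Functional Status Scale and the STAI at baseline. PSS:NICU is collected only then, and so is trait anxiety: "The trait inventory (10 questions, Y2) will be administered only at baseline". The purpose stated for baseline measurement is to check comparability: "The design incorporates extensive measurement of baseline attributes to assess the comparability of intervention and enhanced control groups at inception".

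**The concern.** Under randomisation, a baseline difference between arms is a chance event. Adjustment gains precision when a covariate predicts the outcome, whether or not the arms happen to differ on it. The plan uses the other criterion. Aim 2 shows this most clearly: it recognises that some covariates are known to matter for depression and anxiety, and still leaves them out when the arms look alike.

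Two things are at stake. Precision available from data already collected is used in some realisations of the trial and not in others. And with no list and no threshold, two analysts who both follow the SAP could fit different primary models, each choosing with baseline data by arm in view.

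**Working it through.** **Inputs from the documents.** 150 per arm; five post-baseline measures; correlation 0.50 between repeated measures; alpha 0.05/3 = 0.0167; effect 0.33 SD; stated power 93% (all from Sample Size & Power). The analysis text judges significance by a 95% CI; I keep 0.0167 so that the figures compare with the plan's own.

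**The plan's figure.** Variance of the mean of five measures: v = (1 + 4×0.5)/5 = 0.60. The mean change from baseline has the same variance at this correlation: 0.60 + 1 − 2×0.5 = 0.60. SE = √(0.60×2/150) = 0.0894. Then 0.33/0.0894 − 2.394 = 1.296, so power is 90.2% two-sided. The stated 93% is approached by one-sided 0.0167 (94.1%) or two-sided 0.025 (92.6%). The gap does not affect this point; 90.2% is the unadjusted reference.

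**How often a covariate enters.** The SE of a standardised mean difference (SMD) is √(2/150) = 0.115.

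| Trigger (assumed) | One given covariate enters | At least one of five enters |
|---|---|---|
| p<0.05 | 5% | 1 − 0.95^5 = 23% |
| absolute SMD > 0.10 | 38.6% | 1 − (1 − 0.3865)^5 = 91% |

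At cut-offs of 0.20 and 0.25 a given covariate enters in 8.3% and 3.0% of trials. It is left out more often than not for any cut-off above 0.6745×0.115 = 0.078.

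**Power at 0.33 SD.** Simulation of a linear model on family means, complete data, five independent covariates. R² is their joint share of the variance of the analysed mean and is an assumption.

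| R² | p<0.05 trigger | SMD > 0.10 trigger | Fixed in advance |
|---|---|---|---|
| 10% | 90% | 91% | 92% |
| 20% | 89% | 93% | 95% |
| 30% | 91% | 94% | 98% |

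Differences of a point or so are within simulation error. The closed form for the last column agrees to about one point: SE = √(0.60×(1 − R²)×2/150) = 0.0849, 0.0800, 0.0748, giving 93%, 96%, 98%. At R² 5% the gain is about 1 point.

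**Type I error.** With a fixed list and a fixed threshold, simulated rejection under the null runs from about 0.8% to 1.7% across the settings tried, against a nominal 1.67%. The rule is on the conservative side.

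**What the change score does to R².** Take a trait-like covariate correlated 0.5 with the baseline score and with each follow-up score (assumption), with the plan's 0.50 between scores.
- Share of the post-baseline mean explained: 0.5²/0.60 = 42%.
- Share of the mean change explained: covariance 0.5 − 0.5 = 0, so 0%.
- Share of what remains once the baseline score is in the model: residual variance 0.60 − 0.5² = 0.35; partial covariance 0.5 − 0.5×0.5 = 0.25; covariate variance given baseline 0.75; 0.25²/(0.75×0.35) = 24%.

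The same covariate may therefore contribute nothing or a good deal, depending on whether the baseline score is fitted.

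**The baseline score alone.** If baseline correlates 0.5 with each follow-up score, always fitting it lowers v from 0.60 to 0.35 and raises power at 0.33 SD from 90.2% to 99.3%. That gain belongs to the baseline score and is not evidence for the other covariates.

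**The case against.** The strongest reply is that the loss is small and unproven. The documents give no R² for any covariate, and the plan analyses change. Subtraction can remove most of what a trait-like measure explains, so the loss from omitting MSPSS, PSS:NICU, the Functional Status Scale or STAI trait could be near zero. At the plan's own 0.33 SD, power under the rule stays at about 89% or better in every case above. Nor do the documents show that these measures predict change in self-efficacy. All of this stands, and it limits the claim on size. It does not defend the rule, which still selects on the wrong property and leaves the model open.

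A reader might infer that choosing covariates after seeing data by arm inflates false positives. The documents do not support that. The data consulted are baseline measures, which the Protocol's Consent and Recruitment section places before randomisation, not outcomes, and the null simulations show no inflation. Those simulations assume a fixed list and threshold; a free choice among many covariates and cut-offs was not examined.

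A reader might also infer that covariates almost never enter. That holds for a p<0.05 trigger but not for an SMD cut-off of 0.10, and the plan does not say which applies. Nor do trait anxiety and PSS:NICU lack any stated purpose: the Protocol gives the comparability check as the reason for baseline measurement.

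**Conclusion.** The concern holds as a defect of efficiency and prespecification, not of validity. The covariate rule for Aims 1 and 2 turns on chance imbalance, has no list and no threshold, and leaves the primary model to be settled after the baseline comparison by arm.

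At 0.33 SD the power given up is about 2 to 7 points if the trigger is p<0.05 and about 1 to 4 points if it is an SMD above 0.10, for R² of 10 to 30%; it is about 1 point at R² 5%. These sizes rest on an assumed R² of the analysed mean, five independent covariates, complete data and two-sided alpha 0.0167. On a change outcome without the baseline score in the model, the true loss from omitting the other covariates could be close to nothing. The change should be made because it costs little, not because the trial fails without it.

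**What to change.** In the Statistical Considerations of the SAP, and in the matching Protocol text:

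- Delete the imbalance condition in the opening paragraph, Aim 1 and Aim 2. Keep the baseline table as description only.
- State that every Aim 1 and Aim 2 model includes, whatever balance is observed, the birth-weight stratum, the baseline score of that outcome, and a short named list of prognostic measures already collected. Candidates are MSPSS, PSS:NICU and the Functional Status Scale, with STAI trait added for anxiety and depression. The team should justify the list by expected association with the outcome.
- Do not adopt the list without the baseline score, since the gain on a change outcome could then be near zero.
- Add a rule for missing baseline covariates.
- If adjustment for observed imbalance is still wanted, make it a sensitivity analysis with a stated threshold.

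The cost is wording, a few degrees of freedom out of 300 families, and the missing-covariate rule. No new data are needed.
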